### **‘Survival Time’**

‘Survival Time’, i.e. time to death or time to reaching the criteria for respiratory insufficiency is the other key secondary endpoint. The criteria for respiratory insufficiency are defined as tracheostomy or initiation of non-invasive ventilation for more than 20 hours a day for more than 10 consecutive days, over 48 weeks or 72 weeks, respectively. Descriptive statistics (median and Q1/Q3 quartiles with 95% confidence intervals) and Kaplan-Meier curves will be provided. The difference between oral FAB122 and placebo will be assessed using restricted mean survival time (RMST) analysis for the time point week 48 (and another one for week 72 for the subgroup of 100 patients), adjusting for the stratification variables. The RMST analysis provides robust estimates even when the proportional hazard function is violated.

SAS PROC LIFETEST with option RMST will be used for this analysis.

In addition, a Cox regression model and a stratified log-rank test will also be applied as supportive analysis, including factors for treatment and stratification variables. Patients that complete the study and those that discontinue due to reasons other than death or due to reaching the criteria for respiratory insufficiency will be considered censored.

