**Visit 8 Week 72 (Day 504 ±7Days)-End of Trial visit (first 100 patients enrolled)**

The following procedures will be performed:

- Review ongoing concomitant medications
- Complete physical examination
- Neurological examination
- Weight
- Vital signs measured with the subject in a supine/semi-supine position (for at least 5 minutes prior), including blood pressure, pulse rate, pulse oximetry and temperature
- Standard 12-lead ECG (subject should be in a supine/semi-supine position for at least 5 minutes prior to assessment)

- Fasting blood samples for routine clinical labs (clinical chemistry, haematology). See table 2 for lab assessments
- Urine samples for urinalysis
- Urine pregnancy test only in women of childbearing potential
- Plasma vitamin B6 levels, and, if necessary, vitamin B6 supplements (pyridoxine (100 mg/day)) will be prescribed
- ALS evaluation procedures: ALSFRS-R, Slow Vital Capacity (SVC), Hand-Held Dynamometry, ALSAQ-40, Edinburgh Cognitive and Behavioural ALS Screen (ECAS), EQ-5D-5L, VAS, and King's staging system and MiToS
- Blood sampling for biomarker: neurofilament light (NFL). Creatinine and creatine kinase will be measured in routine biochemistry lab testing.
- Urine collection for biomarkers: urinary extracellular domain of neurotrophin receptor p75 (Urinary P75ECD) and oxidative stress biomarker 8-hydroxyguanosine (8-OHdG)
- Blood sampling for RNA and serum collection for FBR (if consented)
- Blood sampling for FAB122 (if early withdrawal)
- Nerve Conduction Study (NCS) (if required)
- Adverse Events monitoring
- Cost questionnaire
- Compliance check

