#### Cognition

- Proportion of subjects with a change of  $\geq 8$ ,  $\geq 4$ , and  $\geq 9$  for ALS Specific, ALS Non-Specific, and ECAS (Edinburgh Cognitive and behavioural ALS Screen) total score;
- Change from baseline for ALS specific and ALS non specific, and ECAS total score at 24, 48 and 72\* weeks.
- Time to a mean change of  $\geq 8$ ,  $\geq 4$ , and  $\geq 9$  for ALS Specific, ALS Non-Specific, and ECAS total score.

\*All secondary endpoints at 72 weeks will be analyzed for the subgroup of patients that reach 72 weeks (or IE).

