## 4 STUDY ENDPOINTS

### 4.1 Hierarchical multiple testing

A hierarchical multiple testing procedure will be used to evaluate superiority of the primary endpoint, followed by the evaluation of superiority of the key secondary endpoints. A fixed sequence stepwise multiple testing procedure at the 0.05 level will be performed in the following pre-specified hierarchical order:

- I. Primary endpoint: change from baseline ALSFRS-R score after 48 weeks.
- II. Key secondary endpoint: CAFS at 48 weeks
- III. Key secondary endpoint: Survival time (death, tracheostomy or initiation of non-invasive ventilation for more than 20 hours a day for more than 10 consecutive days) over 72 weeks

Each step will be considered confirmatory if all previous steps were successful (i.e. if superiority was achieved). If any of the previous steps were unsuccessful, the subsequent steps are regarded as exploratory.

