### 4.3 Secondary endpoint(s)

All secondary endpoints will be analyzed at 48 weeks including all patients, and additionally at 72 weeks for the subset of patients who reach 72 weeks (or ICE) as a subgroup analysis. The exception will be the planned main analysis for the key secondary endpoint of survival time (see below). This analysis will include data up to 48 weeks for all patients and up to 72 weeks for the subgroup of patients with planned extended follow-up. Analyses conducted at earlier time-points are informative but of lower relevance.

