### **5.6.2 Secondary analysis**

All secondary endpoints at 72 weeks will be analyzed for the subgroup of patients who reach 72 weeks (or ICE). Analysis will be done for the full patient group until week 48, and a separate analysis will be done for the subgroup until week 72.

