## 10.3 End-of-text tables and graphs

Following ICH E3 guidelines, all tables and graphs mentioned here will be presented in Section 14 of the CSR, and tables will be prepared in the order and with section number as stated. Where the column Topline is marked, the output will be part of the Topline results to be supplied shortly after Database lock and will include the results for the full set (until week 48) as well as the subgroup of 100 patients (until week 72) for the secondary analyses.

Table /graph number	Contents of table/graph	Topline
	14.1 Demographic Data Summary figures and tables	
14.1.1	Demographics	X
14.1.2	Baseline characteristics	X
14.1.3	Disposition	X
14.1.4	Medical history	
14.1.5	ALS-specific history	X
14.1.6	Compliance	X
	14.2 Efficacy Data Summary Figures and Tables	
14.2.1.1-14.2.1.x	Descriptive statistics for absolute values and change from baseline ALSFRS-R total score and function domains	X
14.2.1.x	Mean (SD) plot ALSFRS-R total score	
14.2.2.1	Statistical analysis results ALSFRS-R total score (including ICE approaches)	X
14.2.3.1-14.2.3.5	Sensitivity analyses for ALSFRS-R total score	
14.2.4	Statistical analysis results ALSFRS-R function domains	
14.2.5	Descriptive statistics for categorized change from baseline ALSFRS-R total score	
14.2.6	Descriptive statistics for slope of decrease of ALSFRS-R total score	
14.2.7	Descriptive statistics for time to change from baseline for ALSFRS-R total score, including HR (95% CI) and log-rank test	
14.2.8.1	Descriptive statistics for CAFS	X

14.2.8.2	Statistical analysis results CAFS	X
14.2.9.1	Survival time: descriptive statistics	X
14.2.9.2	Survival time: Kaplan-Meier curves	X
14.2.9.3	Survival time: statistical analysis results (RMST)	X
14.2.9.4 - 14.2.9.5	Survival time: supportive analyses (Cox and log-rank)	
14.2.10.1	Overall survival: population alive	
14.2.10.2	Overall survival: Kaplan-Meier curves	
14.2.11.1	Progression-free survival: descriptive statistics	
14.2.11.2	Progression-free survival: Kaplan-Meier curves	
14.2.12	Statistical analysis results joint model	
14.2.13.1- 14.2.13.3	Descriptive statistics for King's staging system	X
14.2.13.4	Kaplan-Meier curves King's staging system	
14.2.14.1- 14.2.14.3	Descriptive statistics for MiToS	X
14.2.14.4	Kaplan-Meier curves MiToS	
14.2.15.1	Descriptive statistics for SVC	
14.2.15.2	Statistical analysis results for SVC	
14.2.16.1	Descriptive statistics for HDD mega score	

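### The SAP declares one combined main survival analysis for step III of the hierarchy, but its methods section specifies only two separate RMST analyses, neither of which is that test

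*SAP*

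**What the plan says.** SAP 4.1 puts survival time third in a fixed sequence at the 0.05 level and defines it with the horizon "more than 10 consecutive days) over 72 weeks". It is confirmatory only if the ALSFRS-R and CAFS steps both succeed.

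SAP 4.3 gives a general rule for secondary endpoints: week 48 in everyone, and week 72 as a subgroup analysis. It then adds: "The exception will be the planned main analysis for the key secondary endpoint of survival time". That analysis uses "data up to 48 weeks for all patients and up to 72 weeks for the subgroup of patients with planned extended follow-up".

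SAP 5.6.2 opens by restating the general rule for all secondary endpoints. The full group is analysed to week 48, and "a separate analysis will be done for the subgroup until week 72". Survival time is not excepted. The ‘Survival Time’ text then plans an RMST "analysis for the time point week 48 (and another one for week 72 for the subgroup of 100 patients", adjusted for the stratification variables, with PROC LIFETEST named as the tool. A Cox model and a stratified log-rank test are supportive.

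SAP 10.3 says that the topline outputs for the secondary analyses cover "the results for the full set (until week 48) as well as the subgroup of 100 patients (until week 72". Table 14.2.9.3, the survival RMST table, is marked as topline.

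Protocol 11.3.4.3 describes an RMST to week 48 with week 72 in brackets, and does not say which of them decides step III.

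**The concern.** A fixed-sequence procedure needs one predefined test at each step. SAP 4.3 describes that test for survival time by its data, and SAP 5.6.2 then plans two others.

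- The week-48 RMST does not have the 72-week horizon of step III.
- The subgroup RMST has the horizon but leaves out about 200 of the 300 patients that SAP 4.3 includes.

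A programmer who follows 5.6.2 produces no RMST that can be reported as step III. Someone would have to choose or build the deciding test later, possibly with results in view. RMST is already the lead method and is not in dispute. The contradiction concerns only the population and time horizon of the confirmatory test.

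**Working it through.** **Texts side by side**

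| Place in SAP | Patients | Horizon | Status |
|---|---|---|---|
| 4.1, step III | not stated | 72 weeks | confirmatory if steps I and II succeed |
| 4.3 | all to week 48, extension patients to week 72, in one analysis | 72 weeks | main analysis |
| 5.6.2, first RMST | all | 48 weeks | not ranked |
| 5.6.2, second RMST | subgroup of 100 | 72 weeks | not ranked |
| 5.6.2, Cox and log-rank | data set not stated | not stated | supportive |

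No row of 5.6.2 gives an RMST that matches 4.3.

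**The plan's own figure.** The documents give no power or event count for survival. The only sample-size statement is for the primary endpoint (difference 3.0, SD 7.5, 2:1, 90% power, two-sided 5%), and it reproduces. The placebo group is 1.5 × (1.960 + 1.282)² × 7.5² / 3.0² = 98.5, so 99, and the total is 297 against 300 stated. Power at 200:100 is 90.4%.

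**Assumptions for survival.** The hazard is constant. The event proportion r at 52 weeks is 10% to 17%. The documents give only an expectation below 17%, for deaths alone (SAP 5.2, Protocol 11.4), and no rate for the composite with respiratory insufficiency. The hazard ratios are also assumed.

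**Expected events with no treatment effect.** The risk by week t is 1 − (1 − r)^(t/52).

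- r = 10%: 9.27% at week 48 and 13.57% at week 72.
- r = 17%: 15.80% at week 48 and 22.74% at week 72.

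| Candidate | Formula | r = 10% | r = 17% |
|---|---|---|---|
| Week 48, all | 300 × risk at 48 | 28 | 47 |
| Week 72, subgroup | 100 × risk at 72 | 14 | 23 |
| Combined | 200 × risk at 48 + 100 × risk at 72 | 32 | 54 |

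**Power.** Simulated Kaplan-Meier RMST difference, unadjusted, 10,000 trials per setting, hazard ratio 0.6, two-sided rejection at 1.96:

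| Candidate | r = 10% | r = 17% |
|---|---|---|
| Week 48, all | 13% | 21% |
| Week 72, subgroup | 8% | 11% |
| Combined | 17% | 29% |

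Counting only rejections that favour active drug, the r = 10% figures are 12%, 6% and 17%; at r = 17% they are unchanged after rounding. At r = 17% and a hazard ratio of 0.8, power to show superiority is 7%, 5% and 9%.

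**Does the choice change the answer?** At a hazard ratio of 0.6, the combined and week-48 tests disagree on significance in 9% to 12% of trials. The combined and subgroup tests disagree in 17% to 25%.

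**False superiority with no effect.** If success on either of the two RMSTs in 5.6.2 counted as step III, the rate would be about 2.6% at 10% events, 3.2% at 17% and 3.4% at 25%, against a nominal 2.5%. The combined test alone gives 2.2% at 17%.

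**The case against.** **SAP 4.3 may simply describe the two analyses in 5.6.2.** This does not stand. The sentence is introduced as the exception to the split rule and refers to a single analysis, so it cannot also be the split rule.

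**SAP 5.6 calls secondary analyses explorative.** The same section keeps the hierarchy of 4.1, under which step III is confirmatory when steps I and II succeed.

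**The Cox and log-rank tests could use the combined data.** This is partly right. The censoring rule in 5.6.2 fits the combined data, and no data set is stated for either test. They are labelled supportive, however, so they cannot be the main analysis.

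**The topline text is weak evidence.** This stands. The sentence in SAP 10.3 covers all secondary analyses and does not mention RMST. The link comes only through Table 14.2.9.3.

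**A reader might infer that SAP 4.3 departs from the protocol and that SAP section 6 fails to record it.** The protocol footnote reads "All secondary endpoints at 72 weeks will be analyzed for the subgroup of patients that reach 72 weeks (or IE", which seems to confine week 72 to the subgroup. But it is an asterisk footnote. In the synopsis and in Protocol 3.2.2, CAFS at 72 weeks carries the asterisk and survival time over 72 weeks does not. Protocol 11.3.4.3 puts no subgroup limit on the week-72 RMST. A departure is therefore not shown, and the silence of section 6 is not an omission.

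**A reader might also infer a multiplicity breach.** No passage allows step III to be claimed on whichever RMST succeeds. The two-sided figure for either test rejecting is about 11%, but most of those rejections favour placebo and part is small-sample error. It should not be quoted as the chance of a false claim.

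**Conclusion.** The contradiction is real and lies within the SAP. Section 4.3 declares one combined main analysis for a confirmatory step, and 5.6.2 specifies two other analyses and no RMST on the combined data.

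The practical size is modest. Under the stated assumptions, reading the subgroup RMST as step III would leave 14 to 23 expected events instead of 32 to 54, and lower power at a hazard ratio of 0.6 from 17%–29% to 8%–11%. The candidates differ clearly only at a large effect, whereas the SAP expects a death rate on active drug that is lower but not substantially so. The hypothetical excess in false superiority is below one percentage point. Step III is also last and conditional.

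The textual finding needs none of these assumptions. The event and power figures depend on the assumed 10% to 17% event rate, constant hazard and hazard ratios, so they should be read as a range. The point should be fixed, but it does not threaten the primary conclusion.

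**What to change.** Before unblinding, amend SAP 5.6.2 (the opening rule and the ‘Survival Time’ text) so that it carries out 4.3:

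1. **Name one step III test.** Use the RMST difference to week 72 in all mITT patients. Censor event-free patients outside the planned extension at their week-48 end of study.
2. **State a truncation rule.** Truncate at the smaller of week 72 and the earlier of the two arms' last follow-up times. This is needed because the final visit has a window: "Visit 8 Week 72 (Day 504 ±7Days". In simulation the truncation time never fell below 71.7 weeks and power at a hazard ratio of 0.6 (17% events) stayed at 29%.
3. **Name the method of adjusting for the stratification factors.** The SAP asks for adjustment and names PROC LIFETEST but does not say how the adjustment is made. Pseudo-value regression is one option: at 17% events and a hazard ratio of 0.6 it gave power of 22%, 10% and 30% for the three candidates, with assumed stratum effects.
4. **Label the week-48 RMST and the 100-patient week-72 RMST as supportive.**
5. **Add the combined result to the topline outputs in SAP 10.3.**

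A note that 4.3 governs the survival analysis is enough. It should not be entered in section 6 as a protocol departure.

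The cost is wording and one more model run. The main downside is that the curve beyond week 48 rests on the first 100 randomised patients, which the supportive subgroup RMST can check. A trend with enrolment order did not inflate error: with the first 100 at 1.5 or 0.67 times the later hazard and no drug effect, false superiority in the combined test was 2.2% and 2.0%.

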### **Other secondary endpoints**

The following secondary endpoints will also be presented, as applicable. No sensitivity analysis, intercurrent event correction or imputation methods will be applied for any of these endpoints.

### **ALSFRS-R score**

Absolute and change from baseline in total ALSFRS-R score after 24 (full group and subgroup) and 72 weeks (subgroup only) will be presented by treatment group in summary tables. Note that results after 12, 48 and 60 weeks for full group/subgroup as available will also be presented by treatment group in the same summary table. The statistical analysis is as described in the section on the primary endpoint.

The proportion of patients with change from baseline in ALSFRS-R score at 24, 48 and 72 weeks will be presented in categories for each treatment group. Categories will include change  $\geq 0$ , change between  $< 0$  and  $\geq -1$ , change between  $< -1$  and  $\geq -2$  etc. A Chi-squared test will be performed, and the p-value added to the table.

The slope of the decrease in ALSFRS-R total score over time at 24, 48 and 72 weeks will be calculated and presented in summary tables. Per treatment arm, slopes will be determined using an MRMM model on the change from baseline, with independent variables treatment group, baseline value, time and treatment\*time interaction. Slopes for each treatment group and slope difference between treatments will be presented. No individual per-patient slopes will be presented.

---

 Where date of death is taken from the Survival follow-up form.

Change from baseline in ALSFRS-R subscale scores will also be calculated after 24, 48 and 72 weeks for the following subscales:

- Bulbar function (question 1-3 of the ALSFRS-R);
- Fine motor function (question 4-6 of the ALSFRS-R);
- Gross motor function (question 7-9 of the ALSFRS-R)
- Respiratory function (question 10-12 of the ALSFRS-R);

Summary statistics for the change from baseline in the above subscale scores will be presented by treatment group and overall, again separately for the full group and the subgroup.

In addition, a similar statistical model as for the primary endpoint will be utilized for analyzing the change from baseline for the subscale scores.

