## 8. PARAMETERS AND METHODS OF ASSESSMENT

### 8.1. Parameters

#### 8.1.1. ALSFRS-R

The ALSFRS-R is a validated 12-item questionnaire designed to evaluate the functioning of respiratory, bulbar, fine and gross motor function in ALS patients. The total score ranges from 48 (no limitation in daily activities) to 0 (total inability). The patients will be asked to complete the ALSFRS-R questionnaire at each in-clinic visit on Screening, Baseline, and weeks 4, 12, 24, 36, 48, 60, and 72, as well on each phone call on weeks 8, 16, 20, 28, 32, 40, and 44. The total score of the ALSFRS-R and the score of each subdomain will be recorded in the eCRF by the investigator or designee.

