### 11.2. Sample Size Determination

The sample size estimation is based on the primary endpoint: the change from baseline in ALSFRS-R score after 48 weeks. A difference of 3.0 points between FAB122 treatment arm and placebo is assumed with a (pooled) standard deviation of 7.5 and an allocation ratio of 2:1 (FAB122:Placebo). With these assumptions, a total sample size of 300 (200 patients on FAB122 and 100 on placebo) is needed to achieve 90% power to detect the difference of 3.0 points between the two treatment groups at a 5% (2-sided) level of significance.

The standard deviation of 7.5 is based on recent study results with edaravone using a similar trial population as applied in this trial, where standard deviations varied between 3.4 and 6.9 (The Writing Group on behalf of the Edaravone (MCI-186) ALS 19 Study Group. 2017 b, 2017;). The variability in this study can be expected to be somewhat higher due to the change of formulation and due to the fact that in this study patient can use riluzole as background therapy.

The hypothesis in this study includes detection of a difference of 3 points in ALSFRS-R at week 48 between the two treatment arms. The patients in the placebo group in ALS studies typically deteriorate by 1 point per month, so 12 points in 12 months. A difference of 3 points therefore corresponds to a 25% difference in deterioration, which is considered clinically significant.

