## 2.4 Sample size

The sample size estimation is based on the primary endpoint: the change from baseline in ALSFRS-R score after 48 weeks. A difference of 3.0 points between FAB122 treatment arm and placebo is assumed with a (pooled) standard deviation of 7.5 and an allocation ratio of 2:1 (FAB122:Placebo). With these assumptions, a total sample size of 300 (200 patients on FAB122 and 100 on placebo) is needed to achieve 90% power to detect the difference of 3.0 points between the two treatment groups at a 5% (2-sided) level of significance.

For further details on the background of these assumptions, refer to the protocol.

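### The chi-squared test on banded ALSFRS-R change ignores the order of the bands, so its printed p-value is weak even if the drug works as planned

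*SAP*

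**What the plan says.** SAP 5.6.2, under ALSFRS-R score, takes the change from baseline at weeks 24, 48 and 72 and says that the proportions "will be presented in categories for each treatment group". The first band is no decline, followed by bands one point wide, and the list ends in an open-ended etc. No lowest band and no pooling rule are given. The comparison is then specified in one sentence: "A Chi-squared test will be performed, and the p-value added to the table". No trend, row-mean-scores or exact version is named, and there is no rule for small expected counts. Protocol 11.3.4.3 leaves the method for each of these endpoints to the SAP, so this sentence is the operative specification.

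For the whole group of other secondary endpoints, the SAP adds: "No sensitivity analysis, intercurrent event correction or imputation methods will be applied for any of these endpoints". Patients who die or drop out before a visit therefore have no band at that visit.

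SAP 5.6 classes everything outside the testing hierarchy as exploratory. The output is Table 14.2.5 in SAP 10.3. It is titled as descriptive statistics and is not marked for the topline results.

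**The concern.** A Pearson chi-squared test on a 2 × K table gives the same p-value however the columns are shuffled. Here the columns are successive amounts of functional loss, and a working drug is expected to move patients along them in one direction. The test spreads its K − 1 degrees of freedom over every possible pattern of difference between the arms, so little is left for the pattern of interest. With one-point bands on a 0 to 48 scale, K is large and many bands hold few patients.

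At stake is only how one exploratory table is read. The SAP chooses to print a p-value, and a reader will take it as some evidence for or against a shift. If the test misses a shift of the planned size more often than it finds it, that p-value tells the reader little.

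**Working it through.** **Inputs from the documents**
- Effect and spread: "A difference of 3.0 points between FAB122 treatment arm and placebo is assumed with a (pooled) standard deviation of 7.5" (SAP 2.4).
- Size: "a total sample size of 300 (200 patients on FAB122 and 100 on placebo) is needed to achieve 90% power", "at a 5% (2-sided) level of significance" (SAP 2.4).
- Placebo decline: "The patients in the placebo group in ALS studies typically deteriorate by 1 point per month, so 12 points in 12 months" (Protocol 11.2). This gives mean changes of −12 on placebo and −9 on FAB122.

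**Inputs assumed, not in the documents**
- All 300 patients contribute.
- Changes are normal and rounded to whole points.
- Every non-empty one-point band is kept.

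**Step 1: reproduce the plan's figure.** The standard error is 7.5 × √(1/100 + 1/200) = 0.9186, and 3.0/0.9186 = 3.266. Power is Φ(3.266 − 1.960) = Φ(1.306) = 0.904. For 90% power the placebo arm needs (1.960 + 1.282)² × (7.5/3.0)² × 1.5 = 98.5, so 99 patients and 297 in total. The stated 90% and 300 are reproduced.

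**Step 2: what the degrees of freedom cost.** The squared signal is 3.266² = 10.67. Treat it as the noncentrality of a chi-squared statistic.
- Spent on 1 degree of freedom (critical value 3.84), it gives 90% power.
- Spread over 29 degrees of freedom (about 30 bands, critical value 42.56), it gives 36%.

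This approximation contains no sparsity at all, so the loss comes from ignoring order.

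**Step 3: simulation.** Pearson chi-squared was compared with a tie-corrected Wilcoxon–Mann–Whitney test on the same bands. There were 10,000 trials for the base, null and skewed cases and 5,000 for the others. The Monte Carlo standard error in the base case is √(0.357 × 0.643/10,000), about 0.5 points.

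| Scenario | Chi-squared | Rank test | Expected counts below 5 |
|---|---|---|---|
| Week 48 base case | 35.7% | 88.6% | 58% |
| No difference (size) | 3.2% | 4.8% | 59% |
| SD 6.9 | 42% | 93% | 54% |
| 17% of each arm lost | 28% | 83% | 67% |
| Right-skewed (gamma) declines | 64% | 98% | 65% |
| Pooled at 20 or more points lost | 38% | 89% | 37% |
| Pooled at 12 or more | 37% | 85% | 32% |
| Pooled at 6 or more | 31% | 68% | 39% |
| Three-point bands | 56% | 89% | 27% |
| Week 24 (assumed −4.5 vs −6, SD 5) | 26% | 65% | 40% |
| Week-72 subgroup, 67:33 (assumed 3.0 points, SD 7.5) | 8% | 43% | 95% |

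The base case had about 30 non-empty bands, and 14% of expected counts were below 1. Pooling the low end cuts sparsity from 58% to 32–39% of cells, yet chi-squared power stays at 31–38%. Sparsity is therefore not the main cause. It does show in the size, where 3.2% against a nominal 5% means the test is conservative.

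**Step 4: the proposed replacement.** A van Elteren test stratified by the two randomisation factors, simulated with the base-case means and SD, gave 87–88% power with size close to 5%. In the 67:33 subgroup it gave about 42%. The strata had no effect on change in this check, so it shows only that stratifying costs almost nothing.

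**The case against.** The strongest reply is that nothing depends on this p-value. The hierarchy in SAP 4.1 contains only the primary endpoint, CAFS at 48 weeks and survival time. The same score is analysed by the MMRM at all three visits, by slopes, by time to 3-, 6-, 9- and 12-point loss, and inside CAFS. A rank test here would add one more p-value on data already well covered. This stands, and it makes the point a minor one. It also makes dropping the p-value as good a remedy as replacing the test.

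A second reply is that 36% and 88% are not properties of the plan. This also stands. They need full data, near-normal changes and unpooled bands, while the SAP leaves the lowest band open and applies no imputation. With right-skewed declines chi-squared power rises to 64%. The ordering of the two tests does not change, however: the rank test was clearly better in every scenario tried.

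Three stronger readings are tempting, and the documents do not support them:
- A reader might infer that a non-significant result here would contradict a positive primary result. An exploratory p-value on a table titled as descriptive contradicts nothing confirmatory.
- A reader might infer that most cells are sparse whatever is done. Under the assumptions used, that holds at week 48 and in the week-72 subgroup if no bands are pooled. It does not hold at week 24 (about 40%), or at week 48 with pooled or wider bands (27–39%).
- A reader might infer that the sparse table produces false positives. The simulated size is below 5%.

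A last objection concerns stratification. Protocol 8.3.1 expects about 90% of patients on riluzole, which leaves about 10 of the 100 week-72 patients without it, to be split by arm and progression rate. Strata there are thin. The simulated stratified test still performed almost as well as the unstratified one (about 42% against 43%), but an unstratified test would be reasonable for that subgroup.

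**Conclusion.** The point holds, as a minor one. A plain chi-squared test on ordered bands is an inefficient choice. Under the plan's week-48 effect, SD and allocation, with complete data, near-normal changes and all one-point bands kept, it has about 36% power against about 88% for a test that uses the order. It would then print a non-significant result in about 64% of trials (100 − 36) in which the drug works exactly as planned. Across the other assumed week-48 scenarios the ranges are about 28–64% and 68–98%. In the week-72 subgroup, with an assumed 3-point difference and the same SD, the figures are about 8% and 43%.

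Ignoring order accounts for most of the loss; sparsity is secondary and depends on the banding. The primary conclusion, the key secondary tests and the overall error rate are untouched.

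**What to change.** In SAP 5.6.2, replace the chi-squared test by one of these:
- a Cochran–Mantel–Haenszel row-mean-scores test with within-stratum ranks (van Elteren), stratified by progression rate and riluzole use; or
- a proportional-odds model with those two factors.

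Allow an unstratified rank test for the 100-patient week-72 subgroup, where strata are thin. In the same edit, define the lowest band and say how patients who died or have no score at the visit are shown in the table.

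Alternatively, delete the p-value and keep the table descriptive, which suits its title and loses nothing that the MMRM does not already provide.

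Either route costs a line or two of SAP text and code, needs no new data, and should be settled before unblinding.
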